**LIST OF ABBREVIATIONS AND RELEVANT DEFINITIONS**

ABR	General Assessment and Registration form (ABR form), the application form that is required for submission to the accredited Ethics Committee; in Dutch: Algemeen Beoordelings- en Registratieformulier (ABR-formulier)
AE	Adverse Event
AR	Adverse Reaction
ATP	Adenosine triphosphate
CA	Competent Authority
CCMO	Central Committee on Research Involving Human Subjects; in Dutch: Centrale Commissie Mensgebonden Onderzoek
CMI	Chronic mesenteric ischemia
CV	Curriculum Vitae
DSMB	Data Safety Monitoring Board
EU	European Union
EudraCT	European drug regulatory affairs Clinical Trials
GCP	Good Clinical Practice
GDPR	General Data Protection Regulation; in Dutch: Algemene Verordening Gegevensbescherming (AVG)
IB	Investigator's Brochure
IC	Informed Consent
IMP	Investigational Medicinal Product
IMPD	Investigational Medicinal Product Dossier
METC	Medical research ethics committee (MREC); in Dutch: medisch-ethische toetsingscommissie (METC)
(S)AE	(Serious) Adverse Event
SPC	Summary of Product Characteristics; in Dutch: officiële productinformatie IB1-tekst
Sponsor	The sponsor is the party that commissions the organisation or performance of the research, for example a pharmaceutical company, academic hospital, scientific organisation or investigator. A party that provides funding for a study but does not commission it is not regarded as the sponsor, but referred to as a subsidising party.
SUSAR	Suspected Unexpected Serious Adverse Reaction
UAVG	Dutch Act on Implementation of the General Data Protection Regulation; in Dutch: Uitvoeringswet AVG

**VLS**      **Visible light spectroscopy**

**WMO**      **Medical Research Involving Human Subjects Act; in Dutch: Wet Medisch-wetenschappelijk Onderzoek met Mensen**

## SUMMARY

**Rationale:** Chronic mesenteric ischemia (CMI) is an incapacitating disease that can progress to potentially fatal acute mesenteric ischemia. The yearly incidence of CMI is 9.2 per 100.000 and will increase due to the aging population and the rising prevalence of cardiovascular risk factors. A gold standard diagnostic test to diagnose CMI is currently lacking, causing both undertreatment and overtreatment of patients and thereby superfluous healthcare expenses. Since oxygen is needed to absorb and metabolise butyrate and glucose in the enterocyte, a  $^{13}\text{C}$ -butyrate and  $^{13}\text{C}$ -glucose breath test could theoretically quantify mucosal oxygen content and thereby identify patients with CMI.

**Objective:** To explore the possibility of detecting mesenteric ischemia by  $^{13}\text{C}$ -butyrate and  $^{13}\text{C}$ -glucose breath testing by comparing timing and concentration of the peak of expired  $^{13}\text{CO}_2$ .

**Study design:** randomised intervention study

**Study population:** healthy human volunteers, >18 old

**Intervention (if applicable):** The intervention group will perform a standardized bicycle ergometry exercise test with a duration of 30 minutes. The aim of the exercise test is to induce temporary mesenteric ischemia.

**Main study parameters/endpoints:** To explore the possibility of detecting mesenteric ischemia by  $^{13}\text{C}$ -butyrate and  $^{13}\text{C}$ -glucose breath testing by comparing timing and concentration of the peak of expired  $^{13}\text{CO}_2$ .

**Nature and extent of the burden and risks associated with participation, benefit and group relatedness:** All participating volunteers will perform 2 breath tests at baseline, 0.5, 1, 1.25, 1.5, 1.75, 2, 2.25, 2.5, 3, 3.5 and 4 hours after ingestion of  $^{13}\text{C}$ -butyrate or  $^{13}\text{C}$ -glucose. A peripheral intravenous cannula will be inserted in patients in the intervention group, in order to obtain a serum blood sample at baseline and after the exercise test. The cannula will also be used to obtain blood for the lactate measurements during the exercise test. Participating volunteers will not experience any benefits of participation. No adverse events are expected and risks associated with participation are deemed very low to non-existent. Insertion of the peripheral intravenous cannula can result in a hematoma.

## 1. INTRODUCTION AND RATIONALE

Chronic mesenteric ischemia (CMI) is an invalidating disease, causing severe complaints of post-prandial pain, food fear and weight loss(1, 2). When left untreated CMI has a substantial risk of bowel infarction in 26-67% of patients, resulting in high mortality and morbidity (3, 4). Diagnosis of CMI remains difficult, since no gold standard diagnostic test exists. The gold standard diagnosis described in current literature is relief of symptoms after endovascular or surgical revascularisation. In order to take treatment decisions a consensus diagnosis is used. Consensus is reached during a multidisciplinary meeting attended by gastroenterologists, vascular surgeons and interventional radiologists. Consensus is based on history, presence of mesenteric artery stenosis on abdominal imaging and in dedicated centres a functional test, such as visible light spectroscopy (VLS) and tonometry. In patients with a consensus diagnosis of CMI based on a stenosis of a single mesenteric artery, treatment is successful in 73% of patients(5). In the remaining 27% not benefitting from treatment, CMI was never the cause of the patients symptoms.

A more accurate functional test detecting intestinal ischemia is of great value to improve the used consensus diagnosis. Current functional tests have several downsides and are therefore not widely used. VLS, a technique measuring mucosal saturations, is limited by a specificity of 60%, causing a substantial amount of false positive test results(6). Tonometry, a technique measuring luminal carbon dioxide concentrations in stomach and jejunum, has a better specificity of 92%(6). Yet this test will cease to exist in a few years, since tonometry equipment is no longer produced. Stressing the urgency of development of a new and improved functional test.

Breath tests are accurate, simple and widely available tests for diseases, such as helicobacter pylori infection and small intestinal bacterial overgrowth(7, 8). Breath tests using glucose and butyrate could possibly be used to diagnose CMI. Butyrate is metabolized by the intestinal epithelium(9). Metabolism of butyrate is oxygen dependent, since oxidation is one of the steps during the production of adenosine triphosphate (ATP).  $^{14}\text{C}$ -butyrate can be used to measure the oxidation rate of butyrate(10). During the oxidation process the  $^{14}\text{C}$  atom is transferred to an oxygen molecule, producing  $^{14}\text{C}$ -carbon dioxide. The labelled carbon dioxide molecule is exhaled and can be measured in the air exhaled by the patient, thereby quantifying the presence of mucosal oxygen.

Administration of deuterated glucose ( $^{13}\text{C}$ -glucose) is a second potential method to measure mucosal oxygen content. Transport of glucose from the lumen into the epithelial cell is driven by an active process consuming ATP and thus oxygen(11). The transport of glucose is driven by a sodium gradient. At the basolateral side of the cell,  $\text{Na}^+/\text{K}^+$ -ATPase extrudes sodium, thereby creating a low sodium concentration within the cell. At the luminal side a  $\text{Na}^+$ /glucose cotransporter, driven by the low intracellular sodium concentration, transports sodium and glucose into the cell. Further transport of glucose into the mesenteric circulation occurs by diffusion facilitated by passive glucose transporters. When  $^{13}\text{C}$ -glucose is metabolized the  $^{13}\text{C}$  atom is transferred to an oxygen molecule, producing  $^{13}\text{C}$ -carbon dioxide. The labelled carbon dioxide molecule is exhaled and can be measured in the air exhaled by the patient.

In subjects with low mucosal oxygen concentrations, the peak in exhaled  $^{13}\text{CO}_2$  of butyrate and glucose is expected to be delayed and lower compared to control subjects with normal mucosal oxygen concentrations. Thereby creating a functional test measuring mucosal oxygen content, which could be of great value in diagnosing CMI.

## 2. OBJECTIVES

Primary Objective:

To explore the possibility of detecting mesenteric ischemia by  $^{13}\text{C}$ -butyrate and  $^{13}\text{C}$ -glucose breath testing by comparing timing and concentration of the peak of expired  $^{13}\text{CO}_2$ .

## 3. STUDY DESIGN

This study is a multi-center randomized interventional proof of principal study, exploring the possibility of quantifying mucosal oxygen content by  $^{13}\text{C}$ -butyrate and  $^{13}\text{C}$ -glucose breath testing.

### *Inclusion*

The study is conducted in healthy volunteers without gastrointestinal complaints and unremarkable medical history. Volunteers are recruited by distribution of patient information folders, containing study information and the investigators contact information, at the gastroenterology and Hepatology outpatient clinics of Erasmus MC University Medical Center and Franciscus Gasthuis & Vlietland. When volunteers contact the investigator the study outline is discussed and inclusion and exclusion criteria are checked. Volunteers are asked whether they have a medical history or are currently experiencing any complaints, they do not undergo additional tests or check-ups to ensure they are healthy. When a healthy volunteer decides to participate in the study an Informed Consent Form will be signed.

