### *Intervention*

Two different intervention groups both consisting of 5 volunteers will be used during the study. The first group will receive  $^{13}\text{C}$ -butyrate, the second group  $^{13}\text{C}$ -glucose. All intervention groups will be performing a standardized bicycle ergometer exercise test with a total duration

of 30 minutes(12). The exercise test has been proven to elicit mesenteric ischemia in athletes. Previous studies suggest an additional 10 minute period of splanchnic hypo perfusion after discontinuation of exercise(13, 14).

The exercise test consist of 3 phases.

- Phase 1: The first 10 minutes of exercise are used to gradually increase the workload until submaximal exercise intensity is reached. Submaximal exercise is defined as lactate between 3 and 5.5 mmol/L. Lactate measurements are performed every 2 minutes, using a rapid lactate measurement kit.
- Phase 2: From minute 10 until 20 submaximal exercise intensity is maintained by adjusting the workload based on lactate measurements. The lactate measurements are performed every 3 minutes.
- Phase 3: Minute 20 until 30 are used to reach maximal exercise intensity. Every 3 minutes the workload is increased by 10% of the submaximal workload until exhaustion. Lactate measurements will be continued with 3 minute intervals.

[figure not shown]

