### **b. Inclusion criteria**

In order to be eligible to participate in this study, a subject must meet all of the following criteria:

- $\geq 18$  years of age
- Experience with cycling
- Signed informed consent
- Unremarkable medical history (no gastrointestinal diseases, no cardiac or pulmonary diseases)
- No gastrointestinal complaints

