## 5. TREATMENT OF SUBJECTS

### 5.1 Investigational product/treatment

#### *Intervention*

Two different intervention groups both consisting of 5 volunteers will be used during the study. The first group will receive  $^{13}\text{C}$ -butyrate and the second group  $^{13}\text{C}$ -glucose. Both intervention groups will be performing a standardized bicycle ergometer exercise test with a total duration of 30 minutes(12). The exercise test has been proven to elicit mesenteric ischemia in athletes. Previous studies suggest an additional 10 minute period of splanchnic hypo perfusion after discontinuation of exercise(13, 14).

The exercise test consist of 3 phases.

- Phase 1: The first 10 minutes of exercise are used to gradually increase the workload until submaximal exercise intensity is reached. Submaximal exercise is defined as lactate between 3 and 5.5 mmol/L. Lactate measurements are performed every 2 minutes, using a rapid lactate measurement kit.
- Phase 2: From minute 10 until 20 submaximal exercise intensity is maintained by adjusting the workload based on lactate measurements. The lactate measurements are performed every 3 minutes.
- Phase 3: Minute 20 until 30 are used to reach maximal exercise intensity. Every 3 minutes the workload is increased by 10% of the submaximal workload until exhaustion. Lactate measurements will be continued with 3 minute intervals.

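### Health is established by questioning alone with no upper age limit, yet half the volunteers cycle to exhaustion and no risk text in the protocol assesses that exercise

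*Combined protocol and SAP*

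**What the plan says.** **Screening.** Section 3 (Inclusion) has volunteers asked whether they have a medical history or current complaints, and then says "they do not undergo additional tests or check-ups to ensure they are healthy". Sections 8.3 and 11.2 repeat this.

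**Eligibility.** The Summary describes the population as "healthy human volunteers, >18 old"; Section 4b sets the limit at 18 or over. Neither gives an upper limit. The health criterion in 4b is "Unremarkable medical history (no gastrointestinal diseases, no cardiac or pulmonary diseases" (the bracket closes there), together with no gastrointestinal complaints. The only criterion touching on fitness is "Experience with cycling", which is not defined. Section 4c excludes pregnancy and inability to sign consent, and nothing else.

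**Exposure.** Sections 3, 5.1 and 8.3 give the same third phase for the exercise groups: "Every 3 minutes the workload is increased by 10% of the submaximal workload until exhaustion". Section 3 supports the test with the statement "The exercise test has been proven to elicit mesenteric ischemia in athletes".

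**Stated risk.** The Summary says "No adverse events are expected and risks associated with participation are deemed very low to non-existent"; the one harm it names is a hematoma from the cannula.

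**The concern.** The risk statement describes a study of tracer doses and a cannula. The study that is described also takes half its volunteers to exhaustion on a bicycle. Whether a risk that low is justified depends on who may enrol, and the criteria leave that open in three ways: age has no ceiling, the wording on medical history can be read narrowly or broadly, and a condition the volunteer does not know about cannot come to light because no check of any kind is made.

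Recruitment adds weight to this. The information folders are distributed at gastroenterology outpatient clinics, where not every reader is healthy, so the criteria and the conversation carry the whole burden of selection. The protocol's own rationale says that the incidence of chronic mesenteric ischemia "will increase due to the aging population and the rising prevalence of cardiovascular risk factors", so age and cardiovascular risk were in view when the protocol was written, but they do not appear among the criteria.

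At stake is the safety of the 10 exercising volunteers and the basis on which an ethics committee accepts the stated risk level. A lesser matter is how much a wide and undefined mix of age and fitness adds to the noise in groups of 5.

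**Working it through.** **1. How many are exposed.** Section 8.2 gives groups BC, BI, GC and GI in 5 blocks of 4.
- Total: 5 × 4 = 20, and 4 groups × 5 = 20. This reproduces the 20 in Section 4d.
- Exercise groups are BI and GI: 2 × 5 = 10, and 10/20 = 50%. Each enrolled volunteer therefore has a one-in-two chance of the exercise test.

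**2. What the criteria stop.**

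| Feature of a volunteer | Barred? | Where |
|---|---|---|
| Known gastrointestinal, cardiac or pulmonary disease | Yes | 4b |
| Gastrointestinal complaints | Yes | 4b |
| Pregnancy; unable to sign consent | Yes | 4c |
| Known vascular disease, hypertension, cardiovascular risk factors | Unclear: outside the bracket, possibly within the general phrase | 4a, 4b |
| Advanced age | No | Summary, 4b |
| Undiagnosed condition | Not detectable by the method used | 3, 8.3, 11.2 |

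**3. What the risk texts cover.**
- Summary, burden and risks: breath tests, the cannula and its hematoma. It mentions the exercise test only as the occasion for blood sampling.
- Section 11.4: side-effects of the two tracers only.
- Structured risk analysis, items a to j: almost entirely about the tracers. Item e says that the effect of exercise-induced ischemia on breath patterns is unstudied. Item g rests on earlier tracer studies in healthy volunteers. Item j expects no effects and says the exercise test can be stopped.

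None of these assesses maximal exercise in adults of unrestricted age.

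**4. What acts later.** Section 8.4 lets a volunteer leave at any time and lets the investigator withdraw one for urgent medical reasons. Section 8.4.1 gives no specific withdrawal criteria. Section 8.7 ends the study for serious health risks. All of these work once a volunteer is already exposed; none works at entry.

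**5. Effect on the comparison.** Section 8.2 describes no stratification by age or fitness, and Section 10.1 compares peak height and area under the curve by an unadjusted t-test or Mann-Whitney test. Sizing the effect would need the share of volunteers with an unlisted or unknown condition and the change that condition makes to a breath curve. The documents give neither, so no figure is computed.

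**The case against.** **The bracket may be illustrative.** Section 4a states the history criterion without the bracket, and Section 3 has volunteers asked about any medical history. A reader might infer that someone with treated hypertension is certain to be admitted, or that any adult at all may enter. Neither follows: such a history should come up when asked about and many investigators would call it remarkable, and several known conditions do bar entry. This part of the objection stands. What remains is that the wording does not settle the question, and that age and undiagnosed conditions are untouched by either reading.

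**The exercise is bounded and can be stopped.** The test lasts 30 minutes. In the last 10, steps of 10% come every 3 minutes: at minutes 23, 26 and 29, or also at minute 20, so 3 or 4 steps and at most 30% to 40% above the submaximal workload. Lactate is followed throughout. This is fair context, but it does not replace selection at entry and does not supply the missing risk assessment.

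**Not testing is an open choice.** It is stated three times and may be reasonable in a small volunteer study. The point is that the stated risk level has to match that choice.

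**A tempting stronger reading concerns the controls.** From the link to ageing and cardiovascular risk one might infer that unscreened controls have low mucosal oxygen and bias the result towards no difference. The documents do not support this. All four groups are randomised from one pool, so impaired volunteers are as likely among exercisers, where they could move the difference the other way. The only frequency given is a yearly incidence of symptomatic disease of 9.2 per 100,000. Used as a probability, it gives 1 − (1 − 0.000092)^10 = 0.09% for at least one case among 10 controls. That does not cover silent disease, but no rate for silent disease is given. The cited papers are visible only as titles, so neither a rate of silent stenosis nor an age range can be taken from them.

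Consent pages are not available, so what volunteers are told about exercise cannot be judged.

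**Conclusion.** The point holds as an inconsistency between who may enrol, what half of them undergo, and the risk that is declared. Its size is 10 of 20 volunteers exposed to exhaustive exercise, after selection by questioning alone, under a risk statement that does not assess it. This rests on the text and needs no assumed prevalence.

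It does not show that unsuitable people will be enrolled, or that the declared risk is wrong; it shows that the documents do not support it. The consequence for the comparison is secondary: wider variability and chance imbalance at 5 per group, with no adjustment planned. No direction of bias is established, and the amount cannot be computed. The sponsor should correct this, mainly for volunteer safety.

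**What to change.** 1. **Sections 4b and 4c.** The sponsor states whether an unremarkable history excludes vascular disease, hypertension and cardiovascular risk factors, and whether an upper age limit applies. The Summary and 4b should also agree on the lower limit (above 18, or 18 and over). The choices are the sponsor's.
2. **Sections 3, 8.3 and 11.2.** Add a short self-completed pre-exercise readiness questionnaire to the existing eligibility conversation, for all four groups and before the envelope is opened. The sponsor defines how positive answers are handled. Timing matters because there are exactly 20 envelopes: a volunteer found unsuitable after opening removes 1 of 5 (20%) from a group, and the list has no spare place. Applying the form to all groups keeps controls and exercisers drawn from the same population.
3. **Summary, Section 11.4 and the structured risk analysis.** Restate the risk so that it covers exhaustive exercise, and bring these texts into line with the eligibility wording.

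The cost is a protocol amendment, a one-page form and slightly slower recruitment. No additional tests, staff or volunteers are needed.

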### *Control*

Two different control groups both consisting of 5 volunteers will be used during the study. The first group will receive  $^{13}\text{C}$ -butyrate and the second group  $^{13}\text{C}$ -glucose. The control groups will perform the breath tests without performing any physical exercise.

### *Intervention*

Two different intervention groups both consisting of 5 volunteers will be used during the study. The first group will receive  $^{13}\text{C}$ -butyrate, the second group  $^{13}\text{C}$ -glucose. All intervention groups will be performing a standardized bicycle ergometer exercise test with a total duration

of 30 minutes(12). The exercise test has been proven to elicit mesenteric ischemia in athletes. Previous studies suggest an additional 10 minute period of splanchnic hypo perfusion after discontinuation of exercise(13, 14).

The exercise test consist of 3 phases.

- Phase 1: The first 10 minutes of exercise are used to gradually increase the workload until submaximal exercise intensity is reached. Submaximal exercise is defined as lactate between 3 and 5.5 mmol/L. Lactate measurements are performed every 2 minutes, using a rapid lactate measurement kit.
- Phase 2: From minute 10 until 20 submaximal exercise intensity is maintained by adjusting the workload based on lactate measurements. The lactate measurements are performed every 3 minutes.
- Phase 3: Minute 20 until 30 are used to reach maximal exercise intensity. Every 3 minutes the workload is increased by 10% of the submaximal workload until exhaustion. Lactate measurements will be continued with 3 minute intervals.

[figure not shown]
#### *Randomisation*

Allocation to the  $^{13}\text{C}$ -butyrate or  $^{13}\text{C}$ -glucose group and allocation to the control or intervention group will be performed by randomisation. Blinding of the healthy volunteers will not be possible, since the intervention group has to perform an exercise test.

#### *Breath test*

Both intervention and control group will perform breath tests at the following time points baseline, 0.5, 1, 1.25 1.5, 1.75, 2, 2.25, 2.5, 3, 3.5 and 4 hours after ingestion of  $^{13}\text{C}$ -butyrate or  $^{13}\text{C}$ -glucose (figure 1). A breath sample is obtained by blowing a single breath of air through a straw into a test tube. Two breath samples are collected at all mentioned time points. The decision to perform breath testing for a total of 4 hours was based on a study that determined  $^{14}\text{CO}_2$  elimination patterns after instillation of butyrate in human caecum and a study describing  $^{13}\text{CO}_2$  elimination patterns in healthy volunteers(10, 15). The tracer could be measured in exhaled air at the first time point, which was 30 minutes after instillation. A peak in expired  $^{14}\text{CO}_2$  was measured after 2 hours. Four hours after instillation approximately 55% of the total  $^{14}\text{CO}_2$  dose had been expired, 24 hours after instillation 70% of the instilled dose had been expired. Since we are interested in the peak of expired  $^{13}\text{CO}_2$  a measurement period of 4 hours seems sufficient, even in the intervention group, in whom a delayed or lower peak is expected. The frequency of breath testing is intensified between 1 and 2.5 hours after ingestion, in order to detect the timing of the  $^{13}\text{CO}_2$  peak more precisely.

Figure 1. timeline collection of breath samples.

